Samples can only be used for research related to safety, PK, and efficacy of the influenza treatment, or influenza disease. They may also be used to develop tests/assays related to influenza treatment, or influenza disease.

Pharmacogenomics analyses may be conducted at the sponsor's discretion and may be reported separately from this study.

STATISTICAL METHODS

The primary analysis will be performed when all randomized subjects have completed the final study visit or discontinued earlier.

Sample Size Determination

The study will enroll 600 subjects between the ages of 13 and 85 years, inclusive. Subjects will be randomized 1:1 to one of the treatment arms.

The sample size is based on the primary endpoint of the hospital recovery scale at Day 6. Based on the proportional odds model and assuming a benefit of approximately 38% reduction of the common odds ratio, a total sample size of 600 subjects (randomized 1:1) is required to obtain 90% power. Inclusion of stratification factors would provide some improvement on the derived power.

Efficacy Analyses

The efficacy endpoints will be analyzed on the Intent-to-Treat-infected (ITT-i) and by randomized treatment.

The ITT-i set consists of all subjects who were randomized and treated and had a confirmed influenza A infection.

Descriptive statistics will be used for all efficacy endpoints and will be tabulated by treatment arm and stratification factors (baseline NEWS2, type of baseline SOC, and time of onset of influenza symptoms).

Subgroup analyses will be performed by, but might not be limited to, treatment extension, region, and age group.

As a confirmatory strategy, to account for multiplicity in the statistical evaluation of the most important efficacy endpoints, a combination of hierarchical testing and the Bonferroni-Holm testing procedure will be applied to control for the overall Type I error rate at the 5% level (2-sided). The following endpoints are included in the confirmatory strategy:

1. Hospital recovery scale at Day 6, ie, primary endpoint
2. Incidence in post-baseline complications
3. Time from start of study drug to hospital discharge
4. Time from ICU admission to ICU discharge

5. Time to return to daily activities
6. Time from start to end of mechanical ventilation
7. Rate of re-hospitalization

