11.4. Efficacy Analyses

Descriptive statistics will be used for all efficacy endpoints and will be tabulated by treatment arm and stratification factors (baseline NEWS2, type of baseline SOC, and time since onset of influenza symptoms). Subgroup analyses will be performed by, but might not be limited to, treatment extension, region and age group.

As a confirmatory strategy, to account for multiplicity in the statistical evaluation of the most important efficacy endpoints, a combination of hierarchical testing and the Bonferroni-Holm testing procedure will be applied to control for the overall Type I error rate at the 5% level (2-sided). The following endpoints are included in the confirmatory strategy:

1. Hospital recovery scale at Day 6, ie, primary endpoint
2. Incidence in post-baseline complications
3. Time from start of study drug to hospital discharge
4. Time from ICU admission to ICU discharge
5. Time to return to daily activities
6. Time from start to end of mechanical ventilation
7. Rate of re-hospitalization

First, the primary endpoint will be tested for superiority of pimodivir in combination with SOC over placebo in combination with SOC at the 2-sided 5% significance level. If superiority is shown on the primary endpoint, then the 2 secondary endpoints indicated by 2. and 3. in the sequence above will be tested for superiority using the Bonferroni-Holm testing procedure: the smallest p-value from the analysis of these 2 secondary endpoints will be compared to a significance level of 0.025 and, if statistically significant (ie, 2-sided $p < 0.025$), then the 2-sided p-value for the second endpoint will be compared to a significance level of 0.05. If both endpoints show superiority, the same Bonferroni-Holm testing procedure will be applied to the 2 secondary endpoints indicated by 4. and 5. in the sequence above. If both these endpoints show superiority, the secondary endpoint indicated by 6. in the sequence above will be tested at the 2-sided 5% significance level. If superiority of this sixth endpoint is shown, the seventh and last endpoint in the sequence above will be tested at the 2-sided 5% significance level.

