2.3. Definition of Subgroups

See [Table 3](#) for the definitions of all the subgroups. The third column in the table indicates for which endpoints the subgroup is applied.

Descriptive statistics will be produced for the different subgroups.

In demographics and baseline disease characteristics, the following subgroups will be used:

- Region
- Influenza A subtype category
- Treatment extension
- Age group
- Time since onset of influenza symptoms (actual: ≤ 72 hours, >72 hours)
- Time since onset of influenza symptoms (actual: ≤ 48 hours, $>48 - 72$ hours, >72 hours)
- Type of SOC at baseline (actual)
- NEWS2 at screening (actual)
- Baseline resistance
- Any baseline polymorphism
- Influenza season
- Study Period
- COVID-19 impacted

Stratification factors (actual) will be used as subgroups for concomitant medication.

For the primary and the six most important secondary endpoints (i.e.: All endpoints included in the hierarchy testing) the subgroup with subgroup*treatment interaction term will be added in the statistical analysis models, except for the study period subgroup, where the analysis will be performed separately for each individual category of the subgroup. For further details see [Section 5.2.3.](#) and [Section 5.3.2.](#) For other endpoints, the statistical analysis will be performed separately for each individual category of the subgroup.

Table 3: Subgroups with their definition

Subgroup	Definition	Endpoints
Region	Based on country according to UN classification of Geographic regions ^[9] : 
 • Europe/Africa • Northern-America • Latin America and the Caribbean • Asia and Oceania 	- Efficacy (primary and secondary endpoints, excluding viral kinetics endpoints)
Age group (years)	
 • 13-17 years • 18-65 years • 66-85 years 	- Efficacy (primary and secondary endpoints, excluding viral kinetics endpoints) - All Safety
NEWS2 at screening (actual)	
 • 4-5 • ≥ 6 	- All Efficacy - Viral Phenotype - Viral Genotype
Type of SOC at baseline (actual)	
 • SOC including influenza antiviral treatment • SOC not including influenza antiviral treatment 	- All Efficacy - Viral Phenotype - Viral Genotype - Safety(AE summary, AEs and SAEs by MedDRA system organ class and preferred term, , influenza-related complications, laboratory toxicity)

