Time (hours) from onset of influenza symptoms to first study drug intake (actual)	
 • ≤ 72 hours • $>72 - 96$ hours 	- All Efficacy - Viral Phenotype - Viral Genotype - Safety(AE summary, AEs and SAEs by MedDRA system organ class and preferred term, , influenza-related complications, laboratory toxicity)
Time (hours) from onset of influenza symptoms to first study drug intake (actual) – 3 categories	
 • ≤ 48 hours • $>48 - 72$ hours • $>72 - 96$ hours 	- All Efficacy - Viral Phenotype - Viral Genotype
Influenza A subtype category	
 • A/H1N1 • A/H3N2 • Other 	- Primary endpoint - The six most important secondary endpoints - All viral kinetics - Viral phenotype - Viral genotype
Hospitalization status	
 • Hospitalized • Outpatient 	- Only CM TLFs
Treatment extension	
 • Extended treatment • No extended treatment 	- All Efficacy - Viral Phenotype - Viral Genotype

Subgroup	Definition	Endpoints
Baseline polymorphism (based on influenza PB2 genotype)	Polymorphism on one or any of these amino-acid positions of interest: 
 • Q306 • F323 • S324 • F325 • S337 • H357 • F363 • K376 • T378 • F404 • Q406 • M431 • N510 	
 - Primary endpoint - Viral Phenotype - Viral Genotype - Viral kinetics
Baseline Resistance (Based on influenza PB2 phenotype)	Based on fold change (FC) in EC ₅₀ for pimodivir: 
 • FC≤4 • FC>4 	
 - Primary endpoint - Viral Phenotype - Viral Genotype - Viral kinetics
Influenza Season	
 • Northern Hemisphere 2017/2018 • Southern Hemisphere 2018 • Northern Hemisphere 2018/2019 • Southern Hemisphere 2019 • Northern Hemisphere 2019/2020 • Southern Hemisphere 2020 and so on to capture all enrolled subjects	
 - Efficacy (primary and the six most important secondary endpoints only) - All viral kinetics - Viral phenotype - Viral genotype

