5.2.3. Analysis Methods

A proportional odds model will be used as primary model to analyze the hospital recovery scale on Day 6, modeling the common odds ratio of improvement on the ordinal scale of active treatment versus placebo. The model will include treatment, hospital recovery scale category at baseline and the stratification factors (NEWS2 category at screening, type of baseline SOC, and time since onset of influenza symptoms). In a first step equal slopes (i.e. proportional odds) for the treatment effect only and unequal slopes for the other covariates, will be modeled. If this model does not fit a full

proportional odds model will be applied, i.e. implying proportional odds for all covariates in the model. The common odds ratio from the final model will be considered as the estimate of the treatment effect. The actual values of the stratification factors will be used for all models, not as randomized. The proportional odds model will be defined in such a way that a common odds ratio smaller than 1 indicates larger improvement in the pimodivir treatment group.

Graphical displays and tabulations will be provided showing the proportion of subjects per hospital recovery scale category and day. Also, shift tabulations will be provided of the baseline hospital recovery scale category versus the post-baseline hospital recovery scale category, per day.

The proportional odds assumption will be assessed by testing for parallel slopes for the treatment effect only.

In addition, each of 5 dichotomizations of the hospital recovery scale, ie,

- Not hospitalized, vs worse (ie, hospitalized)
- Non-ICU hospitalized without supplemental oxygen (or better), vs worse
- Non-ICU hospitalized with supplemental oxygen (or better), vs worse
- In the ICU without invasive mechanical ventilation (or better), vs worse
- Invasive mechanical ventilation (or better), vs worse (ie, died)

will be analyzed using a logistic regression model, including treatment, hospital recovery scale category at baseline and stratification factors.

The hospital recovery scale will also be analyzed using the Van Elteren test with strata defined by the stratification factors^[3, 6].

A table will be created showing the number (%) missing HRS values at day 6 overall and by reason: study discontinuation: due to COVID-19 and not due to COVID-19, discharged against medical advice prior to day 5 and subjects that have no confirmed influenza A.

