The models fitted using the multiple imputation datasets will be the same as the final model on the actual data. The results from the models on the multiple imputation datasets will be combined taking into account the between and within variation of the results.

The analyses on the primary endpoint will be repeated by subgroups for efficacy as defined in Section 2.3. The final model above will be repeated adding these subgroups (defined in Section 2.3) as an additional covariate and interaction with treatment. Per subgroup the common odds ratio and the odds ratios calculated for the dichotomizations will be derived from these models. In addition, for each category in a subgroup, the Van Elteren test with strata defined by the stratification factors will be repeated.

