5.3.1.1. Clinical Outcome

Measurement	Formula
Time to hospital discharge (hours) [Time-to event]	
The time from first study drug intake to first hospital discharge (=event) in hours. Note this excludes time in hospital because of re-hospitalization (a new hospitalization is considered as a re-hospitalization if there is at least 1 day in between the start date of the new hospitalization and the end date of the previous hospitalization) and hospitalizations that ended before first intake.
 
Subjects who complete or withdraw from the study while still hospitalized will be censored at the date of completion or withdrawal. If the time is not available they will be censored at 23:59.
 
If time of end of hospitalization is not known but we have a date of discharge then time will be imputed at 23:59.
 
(Date and time of event or censoring-- date and time of first dose of study drug)/3600, rounded to one decimal.

Time to readiness for hospital discharge (days) [Time-to event]	
The time from first study drug intake until the time to readiness for hospital discharge (= event) in days, with readiness for hospital discharge defined by the investigator. In case at the date of discharge the subject is not ready to be discharged as per investigator assessment, the discharge readiness day will be set to the next day.
 
Censoring of the time will be done analogous to “Time to hospital discharge”, only using the date information, as time is not available for the event.

Total length of hospital stay (hours) [Duration]	
The total number of hours a subject stayed in the hospital during the period from first study drug intake until study termination, calculated as sum of [(end date and time of hospitalization-- start date and time of first intake)/3600], rounded to one decimal for all separate hospital stays per subject. If the time is not available it will be put at 23:59
 
If hospitalization started before first study drug intake, then datetime of first study drug will be used.
 
If hospitalization is still ongoing at study end, the end date and time will be imputed by the end date and time of the last phase as defined in table 1.

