5.3.2. Analysis Methods

Descriptive statistics

The descriptive statistics that will be shown may include the number of subjects, mean, standard deviation, standard error, 95% CI, median, range, interquartile range and geometric mean with corresponding 95% CI.

Kaplan-Meier analysis, Gehan-Wilcoxon test and Log-rank test

All Time-to event variables will be analyzed using a stratified Gehan-Wilcoxon test, a stratified log-rank test and Kaplan-Meier estimates. For endpoints where the start time is not the start of the treatment A summary table including number of subjects included in the analysis, number of subjects censored, 25th and 75th percentiles and median time-to event, with 95% confidence intervals based on log-log transformation method, and the p-values calculated based on the stratified Gehan-Wilcoxon test and stratified log-rank test will be presented.

The data will be presented graphically using the Kaplan-Meier estimate of the survival function by treatment.

For all subgroup analyses, Kaplan-Meier plots will be produced per subgroup and Gehan-Wilcoxon test will be produced for each category of a subgroup.

Accelerated failure time (AFT) model

When indicated, time-to event variables will be compared between pimodivir and placebo using an accelerated failure time (AFT) model. The distribution to be used will be determined based on the goodness of fit of the model using Akaike's information criterion and will be selected from the following parametric families: lognormal, log-logistic, or Weibull. The AFT model will include the fixed, categorical effects for treatment (with placebo as the reference), the time from admission to start of treatment (for the time to hospital discharge and time to hospital discharge readiness) and stratification factors (type of baseline SOC, time of onset of symptoms and screening NEWS2). The scale parameter will be the same across groups

A summary of the final AFT model will include parameter estimates and associated standard errors, estimated accelerated failure time ratios versus placebo and associated 95% confidence intervals, and p-values. The survival curves per treatment group of the accelerated failure time model will also be shown with the Kaplan-Meier plots included in the same output.

For subgroup analyses the survival curves will be shown for each subgroup category separately.

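### The SAP estimates the Day 6 treatment effect by treatment-extension status, a post-randomization variable largely built from the Day 6 scale, which pulls the odds ratio in extended subjects toward 1

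*SAP*

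**What the plan says.** Protocol 4.3 and 9.1.4 place the extension decision at completion of the 5-day course. The subject must have completed treatment and still be in hospital. The subject must also be on invasive ventilation, have room-air SpO2 below 94%, or be at least 3% below a known low pre-influenza level. The investigator must expect benefit and agree to continue the same standard of care. Protocol 9.2.1.1 uses the same 94% and 3% thresholds for HRS category 3 and invasive ventilation for category 5. Protocol 2.1.2 lists the proportion needing extension as a secondary endpoint, and 11.4 compares it between arms.

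On subgroups, protocol 11.4 says "Subgroup analyses will be performed by, but might not be limited to, treatment extension, region and age group", and the synopsis repeats this. SAP 2.3, Table 3 applies treatment extension (extended versus "No extended treatment") to all efficacy endpoints. For the primary and six key secondary endpoints, SAP 2.3 says "the subgroup with subgroup*treatment interaction term will be added in the statistical analysis models", exempting only study period. Other endpoints are analysed separately within each category. For the Day 6 HRS, SAP 5.2.3 adds "The final model above will be repeated adding these subgroups (defined in Section 2.3) as an additional covariate and interaction with treatment", takes a common odds ratio per subgroup and repeats the Van Elteren test in each category. For time-to-event endpoints, SAP 5.3.2 says "Gehan-Wilcoxon test will be produced for each category of a subgroup". Neither the subgroup text nor the estimand text in 5.2.2 says that extension status arises after randomization.

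**The concern.** Randomization does not protect a comparison within a group that is formed by the outcome. If pimodivir works, it moves some subjects out of categories 3-5 and so out of the extended group. Those who remain on pimodivir are there despite treatment, and the comparison with extended placebo subjects understates the effect. The point estimate in extended subjects then drifts toward no effect for a structural reason, while the non-extended estimate stays near the truth. A reader could take this as loss of effect in the patients given a second course.

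Time to hospital discharge has the same structure. It is defined as "The time from first study drug intake to first hospital discharge (=event) in hours", but an extended subject must still be in hospital when extension is decided, so membership depends on the event time.

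**Working it through.** **Inputs from the documents** (protocol 11.3, SAP 1.4): placebo Day 6 distribution 30/30/25/5/5/5% for categories 1-6; common OR 0.62 (38% reduction); N = 600, 1:1; 90% power; 2-sided 5%.

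**Inputs assumed:** the share of each category extended, the correlation between status at the decision and Day 6 status, and the baseline mix. None is in the documents, so each is varied.

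**1. The plan's sample size.** Dividing the placebo cumulative odds of being in category k or better by 0.62 gives pimodivir 40.87/29.89/19.38/3.42/3.28/3.16%. The Whitehead formula is N = 12(z_α/2 + z_β)² / [(ln OR)²(1 − Σp̄³)], where p̄ is the mean category probability over the arms. With (1.960 + 1.282)² = 10.507, (ln 0.62)² = 0.2285 and 1 − Σp̄³ = 0.9175, N = 601.4. The stated 600 is reproduced.

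**2. Base case: all of categories 3-5 extend.** Placebo: 35% of 300 = 105. Pimodivir: 19.38 + 3.42 + 3.28 = 26.08% of 300 = 78. Treatment itself changes who is in the subgroup.

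Within extended subjects, odds of the worse side at each cutpoint:
- Category 4-5 versus 3: pimodivir 6.70/19.38 = 0.346, placebo 10/25 = 0.400, ratio 0.864.
- Category 5 versus 3-4: pimodivir 3.28/22.80 = 0.144, placebo 5/30 = 0.167, ratio 0.863.

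The uniform 0.62 appears as 0.864. The same fit in non-extended subjects (categories 1, 2 and 6) gives 0.675.

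**3. Other uptake patterns.** The first-step model in SAP 5.2.3 has "equal slopes (i.e. proportional odds) for the treatment effect only and unequal slopes for the other covariates". With extension and its treatment interaction as the only additions, this amounts to separate cutpoints per extension level. The fallback is full proportional odds.

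| Who extends | Separate cutpoints: extended / not | Full proportional odds: extended / not |
|---|---|---|
| All of categories 3-5 | 0.864 / 0.675 | 0.933 / 0.668 |
| Half of categories 3-5 | 0.864 / 0.630 | 0.955 / 0.614 |
| All of 3 and 5, half of 4 | 0.858 / 0.659 | 0.946 / 0.647 |
| Half of 3-5, 10% of 2 | 0.789 / 0.625 | 0.892 / 0.604 |

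Extending 30% of category 3 and all of 4 and 5 gives 0.87 in extended subjects with separate cutpoints.

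**4. Looser overlap and covariates** (separate cutpoints, extended subjects):
- Decision on an assumed Day 5 status, latent correlation 0.80-0.98: 0.80-0.83.
- Same distribution at decision and Day 6, correlation 0.7-0.95: 0.78-0.85 (fallback 0.82-0.92).
- Adjusted for baseline HRS, or for one prognostic baseline covariate: 0.76-0.85.

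Over steps 2-4 the extended OR is about 0.76-0.87 and the non-extended OR 0.62-0.69. The fallback gives about 0.82-0.96 in extended subjects.

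**5. Dependence on the true effect.** At a true OR of 0.80, the ratio of extended to non-extended OR is 1.12-1.15 with separate cutpoints. At a true OR of 1 it is 1.00.

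**6. Precision at N = 600, base case.**
- Separate cutpoints: 0.86 (95% CI 0.45-1.66), so SE = ln(1.66/0.45)/3.92 = 0.333. The shift is ln(0.864/0.62) = 0.33, about one SE and half the 95% margin of 0.65.
- Fallback: 0.93 (0.56-1.56), margin 0.51, shift ln(0.933/0.62) = 0.41.
- Interaction power: 9-10% with separate cutpoints, 18-22% in the fallback.

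**The case against.** The strongest reply is that nothing rests on this output. The confirmatory tests use the whole confirmed-infection (ITT-i) set by randomized arm, no claim attaches to a subgroup, extension was pre-specified as a subgroup, and there is no artefact under the null. All of that stands. It limits the seriousness but does not make the estimate interpretable.

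Three stronger readings are tempting and are not supported.

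- **The bias creates a significant/non-significant split.** In the base case the extended CI (0.45-1.66) includes 1 and the non-extended CI (0.46-0.98) does not. But an unbiased 0.62 with SE 0.333 gives 0.32-1.19. A random subgroup of 183 has SE = √[12/(183 × 0.9175)] = 0.267 and CI 0.37-1.05. Both include 1, so subgroup size alone would be expected to produce this pattern. The bias moves the point estimate only.
- **The SAP's first-step model would return a particular value.** That model also carries baseline HRS and three stratification factors. Extended subjects can hardly be in category 1 or 6, so unequal slopes for extension may be inestimable and the fallback may be the model actually used. The ranges are illustrations; in the fallback the attenuation is mostly stronger.
- **Time to discharge would show a false contrast by extension status.** Illustrative calculations showed attenuation in both groups and no clear false contrast. They ignored deaths and did not evaluate the Gehan-Wilcoxon test, the primary time-to-event test. For this endpoint the point is qualitative.

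The overlap with the HRS is also incomplete. Category 4 can be met without hypoxia, investigator judgement applies, and status can change between the decision and the worst-status score on Day 6. Step 4 allows for looser overlap, and the direction holds.

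**Conclusion.** The concern holds as a defect of a planned subgroup analysis. Extension status is a post-randomization outcome that overlaps heavily with the Day 6 HRS. A treatment effect estimated within its levels has no randomized interpretation and is biased in a known direction if the drug works. At the planned effect, 0.62 appears as about 0.76-0.87 in extended and 0.62-0.69 in non-extended subjects with separate cutpoints, and as about 0.82-0.96 in extended subjects under full proportional odds. The direction is firm. The size rests on assumed uptake, decision-to-Day-6 correlation and baseline mix. A single trial would seldom show the contrast as significant. The primary analysis, its type I error and the testing hierarchy are untouched. The change should be made, but the trial's conclusion does not depend on it.

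**What to change.** In SAP 2.3, Table 3 and 5.2.3, remove treatment extension as a treatment-effect or interaction subgroup for the Day 6 HRS. Do the same for endpoints fixed or partly fixed by the time of the extension decision: time to hospital discharge, not hospitalized at Day 6, and HRS on Days 2-5. Show these by arm and extension status only as descriptive tables, labelled as a non-randomized, post-randomization comparison. Label any other efficacy output by extension status the same way. Keep the proportion extended as a secondary endpoint compared between arms. Align the subgroup sentence in protocol 11.4 and the synopsis, or document the departure.

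The cost is wording. Data collection, sample size, extension criteria and confirmatory tests do not change. What is lost is an effect estimate by extension status for those endpoints.
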